7 STATISTICAL ANALYSES

7.1 General Methods

All analysis will be performed in SAS (Statistical Analysis System software, SAS Institute, North Carolina, USA) using version 9.2 or higher. Some figures may be generated using S-Plus.

Continuous variables will be summarized using descriptive statistics, ie, medians, minimums, maximums and means with standard deviations/standard errors of the mean. Some continuous variables may also be summarized using the geometric mean and coefficient of variation. Categorical variables will be summarized by frequencies and percentages. Percentages will be rounded and, therefore, may not always add up to 100. Percentages less than 0.1 will be indicated as “< 0.1”.

Statistical analyses will be presented by part, cohort, or arm as defined in [Figure 6.1-1](#) and [Table 6.2-1](#). Based on the comparability of data in each part, cohort, or arm, any of the groups may be combined to increase the number of subjects for analyses. The grouping schemes for analyses are further described in the DPP.

7.2 Study Conduct

7.2.1 Study Information

Listing:

- Batch number will be listed by batch number and subject. It is noted that a subject may appear multiple times under different batch numbers.

- Randomization code by site will be provided for parts of the study which are randomized (Parts 3 and 4).

7.2.2 *Accrual*

The following will be presented on the All Enrolled Subjects.

Summary:

- Number (%) of subjects accrued by country and investigational site

Listing:

- Subjects accrued by country and investigational site

7.2.3 *Relevant Protocol Deviations*

A relevant protocol deviation is a deviation from the protocol which is programmed in the database and which could potentially affect the interpretability of the study results. Non-programmable relevant eligibility and on-treatment protocol deviations, as well as significant (both programmable and non-programmable) will be reported through ClinSIGHT listings. The following programmable deviations will be considered as relevant protocol deviations and a listing will be provided. During the conduct of the trial, if any relevant protocol deviation is discovered that is not on this list, this SAP should be amended prior to the final database lock. Relevant protocol deviations, their implications, and subsequent actions will be reported in the CSR.

At Entrance:

- Subject enrolled to Cohort 1 and Arms A, B, D, and E and received prior anti-CTLA4 therapy (Inclusion Criteria 2.a.iii).
- Subjects enrolled to Cohort 2 and did not receive prior anti-CTLA4 therapy (Inclusion Criteria 2.a.iv).
- Subjects without measurable disease at baseline (Inclusion Criteria 2.d).
- Subjects with baseline ECOG performance status > 1 (Inclusion Criteria 2.f) at the screening visit only.
- Subjects enrolled in Parts 2, 3, and 4 without BRAF V600 mutation status (Inclusion Criteria 2.i).
- Subjects who have anti-cancer therapy (eg, chemotherapy, biologics, vaccines, radiotherapy, or hormonal treatment) within 4 weeks of study drug administration (Exclusion Criteria 5.c).
- Subjects whose baseline assessments (particularly efficacy assessments) are more than 28 days prior to the start of study therapy

On-Treatment:

- Subjects receiving anti-cancer therapy (chemotherapy, hormonal therapy, immunotherapy regimens, or radiation therapy, standard or investigational) before the last dose of study drug
 - In the event that this occurs, this will be treated as subject's subsequent therapy for certain efficacy assessments described in [Section 4.2.2](#).
- Subjects receiving treatment that is different than what they were assigned or randomized

- In the event that this occurs, subjects will be grouped with the actual received treatment (instead of assigned or randomized treatment) for the analyses.
- For Part 2, subjects whose on-treatment biopsy day relative to the start of study therapy is considerably different than the biopsy window which they were assigned.
 - In the event that this occurs, subjects would be grouped with their actual biopsy window (instead of assigned), or they would be excluded from the grouping schemes comparing the biopsy windows if their on-treatment biopsy is outside the 2 allowable windows.
- During the first dosing visit, if subjects receive ipilimumab dose first, before receiving the nivolumab dose during a visit which a combination therapy is planned.
- Subjects receiving immunosuppressive agents during the course of treatment on or prior to Cycle 2 Day 1 for Part 1 subjects and Week 13 Day 1 for Part 2-4 subjects.
 - In the event that this occurs, pharmacodynamic biomarker analyses may be repeated, as a sensitivity analysis, without these subjects or excluding data points after initiation of immunosuppressive agents.

7.3 Study Population

7.3.1 Subject Disposition

Summary:

- Screening period: The number (%) of subjects of the following will be summarized on the population of All Enrolled Subjects.
 - All enrolled into the study
 - Entering the treatment period
 - Enrolled but not entering the treatment period together with the reasons
- End of treatment period: The number (%) of subjects of the following will be summarized by part, cohort/arm, and overall, based on the population of All Treated Subjects.
 - All treated subjects
 - Subjects continuing in the treatment period
 - Subjects not continuing in the treatment phase together with the reasons
 - Subjects continuing in the study
- End of follow-up period: The number (%) of subjects of the following will be summarized by part, cohort/arm, and overall, based on the population of All Treated Subjects.
 - All treated subjects
 - Subjects continuing to be followed
 - Subjects not continuing to be followed together with the reasons
- End of survival follow-up period: The number (%) of subjects of the following will be summarized by part, cohort/arm, and overall, based on the population of All Treated Subjects.
 - All treated subjects
 - Subjects continuing to be followed

- Subjects not continuing to be followed together with the reasons

Listing:

- Screen failures: Subjects who discontinued from the study pre-treatment for screen failures will be listed with the reason for screen failure
- Subject status at:
 - End of treatment period
 - End of follow-up period
 - End of survival follow-up period
 - End of extension period

7.3.2 Demographic and Baseline Characteristics

The definition of baseline described in [Section 6.1.1](#) will be applied here.

Summary:

The following demographic and baseline characteristics of all treated subjects will be summarized by part, cohort/arm, and overall.

- Age (in years); age category (<65, ≥65)
- Gender
- Race
- Ethnicity (for US only)
- Height
- Baseline Weight
- Baseline Body Mass Index (BMI)
- Baseline ECOG performance status
- Disease characteristics
 - Disease diagnosis, including initial stage/M status and stage/M status at study entry)
 - Subtype of disease
 - Baseline LDH (> ULN vs. ≤ ULN)
 - BRAF mutation status

Listing:

- All relevant data, generally variables listed above
- General medical history
- Tobacco use
- Potential risk factors for pulmonary related events
- Chest X-ray
- Clinical complaints

7.4 Extent of Exposure

The extent of exposure will be characterized according to the number of subjects exposed, the duration of exposure, and the dose to which they were exposed. Analyses in this section will be performed on the population of All Treated Subjects “as treated” as described in [Section 6.2](#).

7.4.1 Study Therapy

The following calculations will not be performed for the subject enrolled in Arm C prior to the closure of that arm in Amendment 06.

Summary:

Descriptive statistics will be provided by part and cohort/arm for the following.

- Nivolumab
 - Number of doses of nivolumab
 - Duration of therapy (weeks) of nivolumab = last dose date - start dose date + 14)/7, only calculated if:
 - ◆ Nivolumab is taken as a monotherapy (Part 1, Arm B, and Arm E)
 - ◆ Nivolumab and ipilimumab combination therapy if the last dose is nivolumab monotherapy (ie, after the 4th dose in Arms A and D).
 - Duration of therapy (weeks) of nivolumab = (last dose date - start dose date + 21)/7, only calculated if:
 - ◆ Nivolumab and ipilimumab combination therapy if the last dose is a combination therapy (ie, the first 4 doses in Arms A and D).
 - Cumulative dose (mg/kg) of nivolumab = the sum of all actual nivolumab doses that a subject received
 - ◆ The actual doses received is documented in mg, so prior to taking the sum, the actual dose needs to be divided by the subject’s weight at baseline, unless their weight at the most recent visit differs by 10% or more compared to baseline
 - Relative dose intensity (%) = cumulative dose (mg/kg) / [3 mg/kg*(last dose date - start dose date + 14)/14]*100, only calculated if nivolumab is taken as a monotherapy (Part 1, Arm B, and Arm E).
 - ◆ Categories: < 50%; 50 - < 70%; 70 - < 90%; 90 - < 110%; ≥ 110%
 - Relative dose intensity (%) = cumulative dose (mg/kg) / [1 mg/kg*(last dose date - start dose date + 21)/21]*100, only calculated if nivolumab is taken as a combination therapy (Arms A and D) and subject’s last dose is in the combo phase.
 - ◆ Categories: < 50%; 50 - < 70%; 70 - < 90%; 90 - < 110%; ≥ 110%
 - Relative dose intensity (%) = cumulative dose (mg/kg) / [1 mg/kg*4 cycles + 3 mg/kg*(last dose date - 84 + 14)/14]*100, only calculated if nivolumab is taken as a combination therapy (Arms A and D) and subject’s last dose is in the mono phase.
 - ◆ Categories: < 50%; 50 - < 70%; 70 - < 90%; 90 - < 110%; ≥ 110%
- Ipilimumab
 - Number of doses of ipilimumab

- Duration of therapy (weeks) of ipilimumab = (last dose date - start dose date + 21)/7.
- Cumulative dose (mg/kg) of ipilimumab = the sum of all actual ipilimumab doses that a subject received
 - ◆ The actual doses received is documented in mg, so prior to taking the sum, the actual dose needs to be divided by the subject's weight at baseline, unless their weight at the most recent visit differs by 10% or more compared to baseline
- Relative dose intensity (%) = cumulative dose (mg/kg) / [3 mg/kg*(last dose date - start dose date + 21)/21]*100
 - ◆ Categories: < 50%; 50 - < 70%; 70 - < 90%; 90 - < 110%; ≥ 110%

In addition, the following will also be summarized.

- Number (%) of treated subjects exposed for specified periods of time such as less than 12 weeks, 12 weeks to 6 months, 6-12 months, and more than 12 months by part and arm.

Listing:

- Drug administration
- Number of doses, duration of therapy, cumulative dose, dose intensity, and relative dose intensity

7.4.2 *Modification of Study Therapy*

Summary:

The following will be provided by part and cohort/arm.

- Nivolumab
 - Number (%) of subjects with dose delay, omission and discontinuation along with the reason
 - Infusion interruptions
 - ◆ Number (%) of subjects with at least one infusion interruption along with the reason*
 - ◆ Duration of interruption*
 - ◆ Number of infusion interruptions per subject
 - ◆ Number (%) of subjects with at least one IV infusion rate reduction along with the reason*
- Ipilimumab
 - Number (%) of subjects with dose delay, omission and discontinuation along with the reason
 - Infusion interruptions
 - ◆ Number (%) of subjects with at least one infusion interruption along with the reason*
 - ◆ Duration of interruption*
 - ◆ Number of infusion interruptions per subject
 - ◆ Number (%) of subjects with at least one IV infusion rate reduction along with the reason*

*More than one reason or one interruption per patient may be counted in these statistics

Listing:

- All relevant information on dose modification listed above

7.4.3 *Prior and Concomitant Medications*

Prior and concomitant medications will be coded using the World Health Organization (WHO) Drug Dictionary. Concomitant medications are defined as medications other than study medications which are taken at any time on-treatment, either with a start date on or after the initiation of study therapy, or with a start date prior to initiation of study therapy and continuing during the study therapy. Concomitant immune modulating medications for adverse event management will be summarized and only include those starting in the on-treatment period.

Summary:

The following prior therapy will be summarized by part, cohort/arm, and overall using frequency statistics.

- Prior therapy, including:
 - Prior surgery
 - Prior radiotherapy
 - Prior systemic cancer therapy
 - ◆ Setting of regimen
 - ◆ Number of prior systemic cancer therapies
 - ◆ Systemic cancer therapy category (BRAF inhibitor, Ipilimumab, IL2, etc.)

In addition, the number (%) of treated subjects for the following will also be provided by part, cohort/arm, and overall, medication class, and generic term.

- Non-study medication summary
- Concomitant immune-modulating medications for management of AE by medication class and generic term

Listing:

- All prior and concomitant medications
- Concomitant immune-modulating medications for management of AE by medication class and generic term
- Subsequent therapy (surgery, radiotherapy, systemic cancer therapy) that occurs after first dose of study drug

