3 INVESTIGATIONAL PLAN

3.1 Study Design and Duration

Study Design: This is an exploratory, open-label, multicenter study of nivolumab and nivolumab in combination with ipilimumab.

Approximately 150 subjects with advanced melanoma (unresectable or metastatic) will be treated in this study in four (4) parts. Part 1 of this study will have two (2) cohorts consisting of approximately 40 patients each: cohort 1 will consist of anti-CTLA4 therapy-naïve patients and cohort 2 will consist of patients who have progressed on an anti-CTLA-4 regimen. Cohorts 1 and 2 will be administered nivolumab at 3 mg/kg dose level every 2 weeks. Subjects will go through a **screening period** of no longer than 28 days and eligible subjects will start the **treatment period** for a duration of 2 years depending on their response. Nivolumab will be administered by IV infusion every 14 days in 56 day cycles (on days 1, 15, 29 and 43 of each cycle). Response assessments will be performed on days 49-56. The response assessment must be completed before the first dose in the next cycle.

In Part 2, approximately 20 anti-CTLA4 therapy-naïve patients will be administered nivolumab at 1 mg/kg and ipilimumab at 3 mg/kg every 3 weeks for 4 doses, followed by nivolumab 3 mg/kg alone every 2 weeks (Arm A). This part of the study is aimed at defining the optimal window for on-treatment biopsy with concurrent nivolumab and ipilimumab therapy. All subjects will be required to undergo a pre-treatment biopsy and consent to on-treatment biopsy. Two (2) groups of approximately 10 patients each will be enrolled sequentially with the first group assigned to an on-treatment biopsy between Days 8 and 15 (weeks 2 and 3) after the start of therapy and the second group assigned to an on-treatment biopsy between Days 22 and 29 (subsequent to the second dose of therapy between weeks 4 and 5) after the start of therapy. Optimal biopsy timing will be defined as the biopsy window with the greatest pharmacodynamic

increase in intratumoral activated T cells compared to the pre-treatment biopsy. The defined optimal on-treatment biopsy window will be used in the third part of this study.

In Part 3, approximately 30 anti-CTLA4 therapy-naive patients will be randomized 2:1 and treated with one of the following:

- Arm A: nivolumab 1 mg/kg IV combined with ipilimumab 3 mg/kg IV Q3W for 4 doses then nivolumab 3 mg/kg IV Q2W
- Arm B: nivolumab 3 mg/kg IV Q2W

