4.3.1 Dose Modifications

There will be no actual dose adjustments allowed for nivolumab or ipilimumab except for weight changes (an increase or decrease of $\geq 10\%$ in weight) at the beginning of each cycle.

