5.3 Safety Assessments

At baseline, a medical history will be obtained to capture relevant underlying conditions. Baseline signs and symptoms are those that are assessed within 2 weeks prior to treatment arm assignment. The baseline physical examination should include: weight, height, ECOG performance status, blood pressure, heart rate, electrocardiogram, O₂ saturation (pulse oximetry) and temperature; it should be performed within 28 days of treatment arm assignment. Concomitant medications will be collected from within 2 weeks prior to treatment arm assignment through the study treatment period (see [Table 5.1A](#), [Table 5.1B](#), [Table 5.1C](#), [Table 5.1D](#), and [Table 5.1E](#)).

Subjects will be considered evaluable for safety if they have received any study drug.

Toxicity assessments will be continuous during the treatment phase and follow-up phases.

Performance status and body weight should be assessed at each on study visit. Vital signs should also be taken as per institutional standard of care prior to, during and after the infusions with investigational products. Pulse oximetry should be done prior to each infusion as well. The start and stop time of the study drug infusion should be documented. If there are any new or worsening clinically significant changes since the last exam, report changes on the appropriate non-serious or serious adverse event page.

Additional measures including non-study required laboratory tests should be performed as clinically indicated.

Safety assessments will be based on the medical review of adverse event reports, results of vital sign measurements, Eastern Cooperative Oncology Group (ECOG) performance status, physical examinations, clinical laboratory results, ECGs, and imaging tests.

The incidence of observed adverse events will be categorized using the most current version of MedDRA and reviewed for potential significance and clinical importance. Adverse events will

be evaluated according to the National Cancer Institute Common Terminology Criteria for Adverse Events (NCI CTCAE) version 4.0.

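### The SAP's rule for converting mg to mg/kg can use a different weight from the one a dose was prepared on, which mis-states cumulative dose and relative dose intensity for some subjects dosed as planned whose weight changes by 10% or more

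*SAP*

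**What the plan says.** SAP 7.4.1 builds cumulative dose in mg/kg from doses recorded in mg. The divisor is the subject's "weight at baseline, unless their weight at the most recent visit differs by 10% or more compared to baseline". The same rule is repeated for ipilimumab. Cumulative dose is the numerator of RDI, which is tabulated with cut-offs at 50, 70, 90 and 110%.

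Protocol 4.3.1 says: "There will be no actual dose adjustments allowed for nivolumab or ipilimumab except for weight changes" of at least 10%, and places that adjustment at the start of each cycle. For Part 1, Protocol 3.1 gives nivolumab "every 14 days in 56 day cycles (on days 1, 15, 29 and 43 of each cycle", so three of the four doses in a cycle do not fall at a cycle start. Weight is nevertheless available between cycle starts. Protocol 5.3 states: "Performance status and body weight should be assessed at each on study visit".

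Three things are left open:
- The protocol does not say which weight the 10% is measured against.
- The SAP does not say which weight replaces baseline, or whether the most recent visit is relative to each dose or to the data cut.
- The protocol defines no cycle for Arms A, B, D and E, although the SAP's RDI denominator for Arms A and D treats each of the four combination doses as a cycle.

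**The concern.** The two rules share a threshold but not a clock. The protocol fixes the mg dose from one cycle start to the next. The SAP lets the divisor move whenever a visit weight crosses 10% from baseline, in either direction. For a dose given as planned, the conversion should return the planned mg/kg, and it does so only if the divisor is the weight on which the dose was calculated.

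There are two ways for it to fail:
- **Crossing in mid-cycle.** The mg dose stays the same, correctly under the protocol, while the divisor switches to the new weight.
- **Returning after a recalculation.** The dose has been reset to a changed weight, the weight then comes back inside 10% of baseline, and the SAP divides the reset dose by the baseline weight.

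In both cases a compliant subject appears over- or under-dosed in the exposure tables. The unstated replacement weight and reference visit also mean that two programmers could produce different tables from the same data.

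**Working it through.** The plan states no cumulative dose or RDI value, so there is no figure to reproduce. The SAP formulas are applied directly, reading the most recent visit as most recent to each dose.

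**Inputs**
- Planned dose 3 mg/kg every 2 weeks, four doses per 56-day cycle (Protocol 3.1 and 4.1).
- Monotherapy RDI = cumulative mg/kg ÷ [3 × (last dose date − first dose date + 14)/14] × 100 (SAP 7.4.1). The denominator is 3 × (42 + 14)/14 = 12 for one cycle and 3 × (98 + 14)/14 = 24 for two.
- Baseline weight 80 kg, hence 240 mg per dose. This is an assumption; only the percentage change matters.

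**Cases the rule handles correctly**
- Weight always within 10% of baseline: 4 × 240/80 = 12, RDI 100%.
- A 10% loss present at Cycle 2 Day 1 with the dose recalculated to 216 mg: 216/72 = 3.00 mg/kg, RDI 100%.

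**Crossing 10% at Day 15, dose unchanged until the next cycle**

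After one cycle, RDI = (3 + 3 × 240/W)/12, where W is the new weight. The correct value is 100% in every row.

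| Weight change | W (kg) | mg/kg credited per dose | RDI after one cycle |
|---|---|---|---|
| −10% | 72 | 3.33 | 108.3% |
| −12% | 70.4 | 3.41 | 110.2% |
| −15% | 68 | 3.53 | 113.2% |
| +10% | 88 | 2.73 | 93.2% |
| +20% | 96 | 2.50 | 87.5% |

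Reaching 110% needs 3.40 mg/kg per affected dose, a loss of 1 − 3/3.4 = 11.8%. Falling below 90% needs less than 2.60 mg/kg, a gain above 3/2.6 − 1 = 15.4%.

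If dose and divisor agree again from Cycle 2, the effect dilutes. A 10% loss gives (15 + 10)/24 = 104.2% after two cycles, 102.1% after four and 100.6% after 52 doses. A 15% loss gives (15 + 3 × 3.529)/24 = 106.6% after two cycles, and a 20% gain gives (15 + 7.5)/24 = 93.8%.

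**Returning inside 10% after a recalculation**

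The dose is reset at Cycle 2 Day 1 for 70.4 kg: 3 × 70.4 = 211.2 mg. Weight then rises to 73 kg, which is 8.75% below baseline. The SAP divisor goes back to 80 kg: 211.2/80 = 2.64 mg/kg. That divisor is neither the dosing weight nor the current weight.
- If only the remaining three doses of Cycle 2 are affected: (5 × 3 + 3 × 2.64)/24 = 95.5%.
- If the protocol's 10% is measured against the last dosing weight, 73 kg is only 2.6/70.4 = 3.7% away and no new recalculation follows. The error then persists. Over 52 doses, RDI = (15 + 47 × 2.64)/156 = 89.2%, dropping below 90% after dose 30.
- On the same reading, with every combination dose a cycle start, ipilimumab reset at dose 2 and 73 kg at doses 3 and 4 gives (3 + 3 + 2.64 + 2.64)/12 = 94.0%.

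**If one latest weight is applied to all doses**

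A subject correctly recalculated at the start of Cycle 4 for a 10% loss gets (12 × 240/72 + 4 × 3)/48 = 108.3% over 16 doses, and 113.2% for a 15% loss.

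**Check of the remedy**

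Dividing each dose by the weight used to calculate it returns 3.00 mg/kg and 100% in all of these 3 mg/kg scenarios.

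**The case against.** The best defence is that the SAP rule tracks the protocol closely. Baseline weight is the default and the exception uses the protocol's own threshold. A reader might infer that the SAP generally converts with the latest weight, or that exposure is wrong for subjects dosed as planned as a group. The documents do not support either. On the per-dose reading, subjects who stay within 10% of baseline, or who are recalculated at a cycle start and then stay stable, convert exactly.

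A reader might also extend the mid-cycle problem to every cohort and arm. That is not shown. A multi-dose cycle is defined only for Part 1. If each combination dose is a cycle, as the SAP's denominator implies, no combination dose falls in mid-cycle. The every-2-weeks dosing in Arms A, B, D and E depends on a cycle that the protocol does not define.

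The category shifts in the table need a large change within two weeks of the first dose and a subject who stops after one cycle. One further aligned cycle returns the 15% loss and the 20% gain to the 90 to under 110% band. Persistence after a regain depends on an unstated reference weight. If that reference is baseline, a return inside 10% may restore the baseline dose at the next cycle start, and the SAP divisor would then agree with it.

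All of this limits the reach of the point. It does not remove the mismatch: a compliant dose can still be divided by a weight on which it was not prepared.

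**Conclusion.** The point holds as a narrow defect in a stated derivation. It affects some subjects dosed as planned: mainly Part 1 subjects at least 10% off baseline at a mid-cycle visit, and subjects who come back within 10% after a recalculation. For a 10% change from Day 15, RDI after one cycle is off by about 7 to 8 percentage points (93.2% or 108.3%). After a reset at 70.4 kg and partial regain, each later affected dose is credited 12% too low. The error usually shrinks with follow-up and seldom moves a subject to another RDI category; the exception is a regain that persists under one possible reading of the protocol's 10%.

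The quantities are descriptive exposure summaries. They do not enter the primary biomarker analysis, and drug administration is listed by subject. It is tempting to add that the error is frequent or concentrated in sicker subjects. The documents give no distribution of weight change and do not link it to prognosis, so neither can be claimed and the number affected cannot be computed. The figures assume 80 kg at baseline for illustration and, except where stated, the per-dose reading of the most recent visit.

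**What to change.** In SAP 7.4.1, for both drugs, divide each administered mg dose by the weight used to calculate that dose. Take the recorded dosing weight or, if none is recorded, the visit weight at the last recalculation. Delete the comparison with the most recent visit.

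The fallback cannot be programmed until SAP 7.4.1 and Protocol 4.3.1 are reconciled on two matters: which weight the 10% refers to, and what counts as a cycle in Arms A, B, D and E. This clarifies the derivation and need not change any dosing rule.

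The cost is a short SAP edit, one changed derivation and a small amount of extra programming. Visit weights are already collected. The text available for review does not show that a dosing weight is recorded, so that should be checked first.

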4.3.4 Dose Delay Criteria

Study drug administration should be interrupted and increased monitoring of subjects should ensue if any of the following drug related adverse event(s) occurs:

- Any persistent grade ≥ 2 non laboratory non-skin drug related adverse event except for fatigue and weakness
- Any grade ≥ 2 endocrine drug-related adverse event
- Any grade ≥ 3 skin drug related adverse event

- Any Grade ≥ 3 drug-related laboratory abnormality (except lymphopenia, asymptomatic lipase or amylase increases, or any electrolyte abnormality without any clinical sequelae that is either spontaneously reversible or resolves with clinical management to grade 2 or less within 72 hours)
- ALT or AST $> 3X$ ULN (treatment may resume when the AE resolves to Grade 1)
- Patients with pre-existing neurologic or ophthalmologic anti-CTLA4 related adverse event who develop clinical symptoms leading to a 1 grade drug related shift (i.e. grade 1 to grade 2)
- Any AE, laboratory abnormality or inter-current illness which, in the judgment of the investigator, warrants skipping the dose of study medication

If dose delay is necessary, both nivolumab and ipilimumab must be delayed until treatment can resume. If a delay prevents subsequent infusion of ipilimumab, the dose of ipilimumab should be replaced as soon as possible. At least 19 days must elapse between the replacement dose of ipilimumab and the administration of the next dose of the combination.

The occurrence of clinically meaningful drug related AEs requires early recognition and prompt intervention. Management algorithms are available for suspected pulmonary, gastrointestinal, hepatic, renal, endocrine, neurological and skin toxicities. The recommendation is to follow the nivolumab IB adverse event algorithm. The algorithms can also be found on [Appendix 4](#).

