4.3.5 Study Drug Discontinuation Criteria due to Adverse Event(s)

Study drug administration must be discontinued if at least one of the following drug related adverse event(s) occurs:

- Any \geq Grade 2 eye pain or reduction of visual acuity that does not respond to topical therapy and does not improve to Grade 1 severity within 2 weeks of starting therapy OR requires systemic treatment;
- Any \geq Grade 3 non laboratory drug-related adverse event with the exception of fatigue, and endocrine drug related AEs which are stable with hormone replacement therapy
- Any \geq Grade 3 bronchospasm, hypersensitivity reaction, or infusion reaction;
- Any patient that experiences any grade allergic/infusion reaction while receiving study drug at a slower infusion rate and/or with premedication due to a prior allergic/infusion reaction
- Any drug-related Grade 4 laboratory abnormalities, (except lymphopenia, asymptomatic lipase or amylase increases, or any electrolyte abnormality without any clinical sequelae that is either spontaneously reversible or resolves with clinical management to grade 2 or less within 72 hours)

- Hepatotoxicity as evidenced by any of the following:
 - AST or ALT > 5 - 10x ULN for >2 weeks
 - AST or ALT > 10 ULN
 - Total bilirubin > 5 x ULN
 - Concurrent AST or ALT > 3 x ULN and total bilirubin > 2 ULN (potential Hy's Law case)
- Any adverse event, laboratory abnormality or intercurrent illness, which in the judgment of the Investigator, presents a substantial clinical risk to the subject
- All adverse events that meet discontinuation criteria, as well as any Grade 3 or 4 infusion reactions must be reported to BMS, within 24 hours using the rapid notification procedures described in [Section 6.1.1](#).

Subjects who experience AEs that require discontinuation while receiving both nivolumab and ipilimumab may be allowed to continue therapy with nivolumab only if deemed in their best interest by both the PI and the BMS medical monitor. This will be decided on a case by case basis and will require convincing evidence that the benefit outweighs the risk.

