4.3.9 Infusion Delays and Missed Doses

In the case that an infusion cannot be administered at a scheduled visit, it should be administered as soon as possible. If the delay is between 1 and 7 days, the procedures at the original scheduled

visit should be performed. If the delay is more than 7 days, the infusion at the original scheduled visit will be considered a missed dose, and the procedures at the next visit should be performed. Response assessments must never be omitted. Subsequent visits will follow accordingly from the actual date of last study drug administration. Subjects with infusion delays ≥ 8 weeks should normally discontinue treatment and enter the follow-up period with the exception of delays as described in [Section 4.3.6](#) and after specific consultation and agreement between the investigator and BMS Medical Monitor in settings where benefit/risk may justify continued study therapy.

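### SAP 7.4.1: the nivolumab relative dose intensity formula for Arm A/D subjects whose last dose is in the monotherapy phase omits the start dose date

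*SAP*

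**What the plan says.** SAP 7.4.1 (Study Therapy) gives four RDI formulas. Each divides the cumulative dose received by the dose planned over the time on drug.

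- Nivolumab monotherapy (Part 1, Arms B and E), denominator ending "3 mg/kg*(last dose date - start dose date + 14)/14]*100".
- Nivolumab in Arms A and D, last dose in the combination phase, denominator ending "1 mg/kg*(last dose date - start dose date + 21)/21]*100".
- Ipilimumab, denominator ending "3 mg/kg*(last dose date - start dose date + 21)/21]*100".
- Nivolumab in Arms A and D, last dose in the monotherapy phase: "cumulative dose (mg/kg) / [1 mg/kg*4 cycles + 3 mg/kg*(last dose date - 84 + 14)/14]*100".

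The first three measure elapsed time from the start dose date. The fourth has no start dose date. The duration-of-therapy formula in the same section, for the same Arm A/D subjects, does subtract it. Neither document redefines the last dose date as a study day.

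RDI is reported by part and cohort/arm in five categories, from below 50% to 110% or more, and is also listed by subject.

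**The concern.** The 84 in the fourth formula is the planned length of the combination phase: four doses, 21 days apart. It makes sense only when taken from days since first dose. Without the start date, the formula subtracts it from a date, so the planned dose depends on the calendar and not on the subject's treatment time.

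This formula summarises delivered against planned nivolumab for the combination subjects who reached monotherapy. SAP Table 6.2-1 plans about 40 subjects in Arm A (10 + 10 + 20) and about 10 in Arm D. The documents do not predict how many of these reach the monotherapy phase.

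**Working it through.** The documents state no numerical RDI, so there is no figure to reproduce. The natural check is a subject dosed exactly as planned, whose RDI should be 100%.

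**Inputs.** Regimen (SAP 2.1): nivolumab 1 mg/kg every 3 weeks for four doses, then 3 mg/kg every 2 weeks. Protocol Table 5.1D puts the first monotherapy dose at Week 13 Day 1, which is 12 × 7 = 84 days after first dose. Combination doses therefore fall on days 0, 21, 42 and 63, and the k-th monotherapy dose on day T = 84 + 14(k − 1). The dose received is 4 + 3k mg/kg. SAP 7.1 names SAS as the software; SAS stores a date as days since 1 January 1960. First-dose dates of 1 January 2013 and 1 January 2015 are assumptions, used only to give a size.

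**The other three formulas, n doses on schedule.**
- Nivolumab monotherapy: 3n / [3 × (14(n − 1) + 14)/14] = 3n/3n = 100%.
- Nivolumab, combination phase: n / [(21(n − 1) + 21)/21] = n/n = 100%.
- Ipilimumab: 3n / [3 × (21(n − 1) + 21)/21] = 3n/3n = 100%.

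**The fourth formula.** Let L be the last dose date and S the start dose date.
- Printed: denominator = 4 + 3(L − 84 + 14)/14.
- Literal reading, k = 1, first dose 1 January 2013: S = 53 × 365 + 14 leap days = 19,359; L = 19,359 + 84 = 19,443; denominator = 4 + 3 × 19,373/14 = 4,155.4 mg/kg; RDI = 7/4,155.4 = 0.17%.
- Study-day reading (day 1 = first dose), k = 1: L = 85; denominator = 4 + 3 × 15/14 = 7.214; RDI = 7/7.214 = 97.03%. The denominator is too large by 3/14 = 0.214 mg/kg at every k.
- Start date inserted: denominator = 4 + 3(L − S − 84 + 14)/14 = 4 + 3(T − 70)/14 = 4 + 3k; RDI = 100%.

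| Monotherapy doses k | Day T | Dose received (mg/kg) | Literal, 2013 start | Literal, 2015 start | Study-day reading | Start date inserted |
|---|---|---|---|---|---|---|
| 1 | 84 | 7 | 7/4155.4 = 0.17% | 7/4311.8 = 0.16% | 7/7.214 = 97.03% | 7/7 = 100% |
| 7 | 168 | 25 | 25/4173.4 = 0.60% | 25/4329.8 = 0.58% | 25/25.214 = 99.15% | 25/25 = 100% |
| 20 | 350 | 64 | 64/4212.4 = 1.52% | 64/4368.8 = 1.46% | 64/64.214 = 99.67% | 64/64 = 100% |
| 46 | 714 | 142 | 142/4290.4 = 3.31% | 142/4446.8 = 3.19% | 142/142.214 = 99.85% | 142/142 = 100% |

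The literal reading puts every fully compliant subject below 50%. The study-day reading leaves them in the 90% to below 110% category but does not return 100%.

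**The case against.** The best defence is that this is a one-term slip whose repair is plain from the neighbouring formulas. A literal program would give values so absurd that any check would catch them, and the study-day reading changes no category for an on-schedule subject. The output is descriptive, and the number of doses, duration, cumulative dose, delays and omissions are all reported separately. All of that stands and limits the importance of the point. It does not make the printed formula right: the SAP is the specification, and as written it does not give a valid RDI.

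Two stronger readings are tempting, but the documents do not support them.

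**That the repaired formula still clashes with the combination-phase formula when doses slip.** Protocol 4.3.9 says "Subsequent visits will follow accordingly from the actual date of last study drug administration". If all four combination doses are given and the fourth slips from day 63 to day 70, the combination-phase formula gives 4/[(70 + 21)/21] = 92.3%. One monotherapy dose on day 91 then gives 7/[4 + 3 × (91 − 70)/14] = 7/8.5 = 82.4%. This is a choice of reference, not an error. The printed four cycles and 84 days already largely fix that reference as a planned 84-day combination phase followed by 3 mg/kg per 14 days, and a lower RDI after a delay is what RDI is meant to show. The two formulas are split by the phase of the last dose, so they never both apply to one subject in the same analysis.

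**That subjects who stop the combination early should be excluded from the formula.** Protocol 4.3.5 states: "Subjects who experience AEs that require discontinuation while receiving both nivolumab and ipilimumab may be allowed to continue therapy with nivolumab only". The fixed four cycles and 84 days do not fit them if they had fewer than four combination doses. For example, the repaired denominator drops below 4 mg/kg when the last dose is less than 70 days after the first. SAP 7.4.1 partly addresses this by describing the monotherapy phase as following the fourth dose, but does not settle these subjects. Excluding them would selectively remove people who stopped the combination for toxicity from the RDI summary, and nothing in the documents calls for that.

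**Conclusion.** The formula is wrong as printed and should be corrected. For an on-schedule subject it returns about 0.2% to 3% if a calendar date is used, or 97.03% to 99.85% if a study day is used, where 100% is due. The size of the literal result rests on SAS dates and the assumed 2013 and 2015 first doses; any recent calendar date leaves RDI far below 50%. The study-day figures assume first dose is day 1. If elapsed days were meant, the printed formula would equal the repaired one, but the SAP does not say so.

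A reader might infer that RDI in the combination arms cannot be computed, or that each programmer would have to guess. That goes too far, because the adjacent formulas show the missing term. Nor does the omission reach any conclusion of the trial: RDI enters an exposure summary and a listing, and no primary biomarker or efficacy analysis uses it. Early combination stoppers are a separate, smaller gap in the SAP, whose frequency and timing the documents do not give.

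**What to change.** In SAP 7.4.1, subtract the start dose date inside the bracket of the monotherapy-phase formula. With L and S as above, the denominator becomes `1 mg/kg × 4 cycles + 3 mg/kg × (L − S − 84 + 14)/14`. This returns exactly 100% for on-schedule subjects and matches the other three formulas. Check that the corresponding program line uses it.

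At the same time, reconcile SAP 7.4.1 with Protocol 4.3.5 so that it is clear how RDI is handled for subjects who continue nivolumab alone after fewer than four combination doses. No exclusion is proposed.

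The cost is one term in the SAP and the matching program line. The neighbouring formulas already use the dosing dates, so no new data are needed.
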